NYHA classification of cardiac performance	
Classification of cardiac performance developed by New York Heart Association, which classifies the severity of heart failure into 4 classes based on the subjective symptoms.
 
<NYHA classification of cardiac performance>
 
  
 Class I	No limitations of physical activities. Ordinary physical activity does not cause undue fatigue, palpitations, dyspnea, or angina pectoris.	
 
 Class II	Slight limitation of physical activity. Asymptomatic at rest. Ordinary physical activity results in fatigue, palpitations, dyspnea, or angina pectoris.	
 
 Class III	Marked limitation of physical activity. Asymptomatic at rest. Less than ordinary physical activity leads to fatigue, palpitations, dyspnea, or angina pectoris.	
 
 Class IV	Inability to carry on any physical activity without discomfort. Symptoms of heart failure or angina pectoris present at rest. These symptoms may be exacerbated by a slight exertion.	
  
	Class I	No limitations of physical activities. Ordinary physical activity does not cause undue fatigue, palpitations, dyspnea, or angina pectoris.	Class II	Slight limitation of physical activity. Asymptomatic at rest. Ordinary physical activity results in fatigue, palpitations, dyspnea, or angina pectoris.	Class III	Marked limitation of physical activity. Asymptomatic at rest. Less than ordinary physical activity leads to fatigue, palpitations, dyspnea, or angina pectoris.	Class IV	Inability to carry on any physical activity without discomfort. Symptoms of heart failure or angina pectoris present at rest. These symptoms may be exacerbated by a slight exertion.	NYHA
Class I	No limitations of physical activities. Ordinary physical activity does not cause undue fatigue, palpitations, dyspnea, or angina pectoris.									
Class II	Slight limitation of physical activity. Asymptomatic at rest. Ordinary physical activity results in fatigue, palpitations, dyspnea, or angina pectoris.									
Class III	Marked limitation of physical activity. Asymptomatic at rest. Less than ordinary physical activity leads to fatigue, palpitations, dyspnea, or angina pectoris.									
Class IV	Inability to carry on any physical activity without discomfort. Symptoms of heart failure or angina pectoris present at rest. These symptoms may be exacerbated by a slight exertion.									
Paravalvular regurgitation	
All blood leakages around the prosthetic valve associated with the gap between the prosthetic valve and native annulus.
 
Paravalvular regurgitation can be classified as follows:
 
Total regurgitation: Moderate to severe paravalvular dysfunction clearly observed by echocardiography.
 
Mild regurgitation: Paravalvular regurgitation classified as aortic valve regurgitation < 3+ and not requiring surgical intervention.
 
Severe regurgitation: Aortic valve regurgitation $\geq 3+$ and requiring surgical intervention.
 
(also see "Non-structural dysfunction")
	STS/AATS								
Pre-procedural complication	Defined as any complication developed before the start of the study procedure and the symptoms sustained or under treatment at the start of the study procedure.									

Term	Definition	Reference/rationale												
Prosthesis-patient mismatch (PPM)	
Prosthesis-patient mismatch (PPM) is an index to show a relationship between the implanted prosthetic valve and cardiac output originally required for the subject. When the aortic flow velocity coefficient by continuous wave Doppler method is normal (> 0.35), but $EOAi \leq 0.85$ ($BMI < 30$), it is regarded as hemodynamically significant prosthesis-patient mismatch.
 
  
 	Not significant	Moderate	Severe	
   
 $EOAi$ (cm^2/m^2)	> 0.85	$0.85 - 0.65$	< 0.65	
 
 $BMI \geq 30$ (kg/cm^2)	> 0.70	$0.90 - 0.60$	< 0.60	
  
		Not significant	Moderate	Severe	$EOAi$ (cm^2/m^2)	> 0.85	$0.85 - 0.65$	< 0.65	$BMI \geq 30$ (kg/cm^2)	> 0.70	$0.90 - 0.60$	< 0.60	VARC-2
	Not significant	Moderate	Severe											
$EOAi$ (cm^2/m^2)	> 0.85	$0.85 - 0.65$	< 0.65											
$BMI \geq 30$ (kg/cm^2)	> 0.70	$0.90 - 0.60$	< 0.60											
Re-hospitalization	
Re-hospitalized due to AS symptoms and/or post-procedural complication.
 
If the post-procedural hospital stay exceeds 30 days, in-hospital Day 31 is statistically regarded as re-hospitalization.
													
Re-intervention	All interventions including repair, correction, or replacement of the already operated valve.	STS/AATS												
Stroke/transient ischemic attack	
<Stroke/transient ischemic attack diagnostic criteria>
 
Acute onset of a local or general neurological disorder, with at least one of the followings: changes in the conscious level, hemiplegia, hemiparesis, numbness, sensory loss affecting one side of the body, dysphasia or aphasia, hemianopia, amaurosis fugax, and other neurological signs or symptoms consistent with stroke.
 
Stroke: Local or general neurological disorder sustains ≥ 24 hours, or even < 24 hours new hemorrhage or infarction is found by head neuroimaging, or a neurological disorder resulted in death.
 
Transient ischemic attack: Local or general neurological disorder sustains < 24 hours, with no new hemorrhage or infarction by head neuroimaging.
 
As for clinical findings, the absence of causes other than stroke that can be easily identified (brain tumor, trauma, infection, hypoglycemia, peripheral lesion, influence of drug, etc.) must have been determined by a neurologist or together with a neurologist*. Definitive diagnosis should be made by at least one of the followings:
 
 • Diagnosis by a neurologist or neurosurgeon • Head neuroimaging (CT scan or brain MRI); however stroke may be diagnosed only by the clinical findings 
* Do not report non-local encephalopathy as stroke, unless findings of cerebral infarction are present based on the head neuroimaging (CT scan or brain MRI).
 
<Stroke classification>
 
Ischemic: Acute angiopathy at the local brain, spinal cord, or retina associated with infarction in the central nervous system tissues
 
Hemorrhagic: Acute angiopathy at the local or general brain or spinal cord associated with hemorrhage in the cerebral parenchyma, cerebral ventricle, or
	VARC-2												

Term	Definition	Reference/rationale
	
subarachnoid
 
If the information is inadequate for determining ischemic or hemorrhagic, classify as cause unknown.
 
<Definition of stroke> Stroke is classified into disabling or non-disabling.
 
 • Disabling stroke At 90 days after the onset of a stroke, $mRS \geq 2$, and exacerbation ≥ 1 in the mRS from before the onset. • Non-disabling stroke At 90 days after the onset of a stroke, $mRS < 2$, and no exacerbation ≥ 1 in the mRS from before the onset. 	
Structural valve deterioration	
All changes in the functions of the implanted valve resulted from abnormally specific to the valve that may lead to stenosis or regurgitation (exacerbation ≥ 1 of NYHA classification of cardiac performance).
 
Structural valve deterioration includes dysfunction or degradation of the implanted valve, while infection or thrombosis confirmed by re-operation, autopsy, or laboratory tests is not included. Structural deterioration means substantial change in the valve, including wear, damage, calcification, rupture of the cusp, and fraying of the joining thread for the components (e.g.: cusp).
	STS/AATS
Valve thrombosis	All thrombi adhered to the implanted valve or around the valve that obstruct part of the blood flow paths, or interfere with valve functions, or are large enough to be treated. Valve-related thrombus observed at autopsy of a death case that was assessed as unrelated to the study device will not be regarded as valve thrombosis.	VARC-2
Unplanned use of artificial heart-lung machines	Cases for which artificial heart-lung machines were used unplanned for circulatory assistance during study procedure.	VARC-2
Valve implant analysis set	The subject population consisting for all subjects in whom the THV was implanted, and when the subject exited the operation room the implanted THV was maintained is defined as valve implant (VI) analysis set. Subjects for whom the investigational valve was not implanted, including subjects switching to surgery, and TAVI bioprosthetic valve other than the investigational valve was implanted, will not be included in the VI analysis set. As for subjects who received a valve-in-valve procedure, cases with additional investigational valve implantation will be included in the VI analysis set, while cases with additional TAVI bioprosthetic valve other than the investigational valve will be excluded from the VI analysis set.	
Valve-in-valve procedure	Implantation of a new prosthetic valve in the already implanted prosthetic valve during or after the study procedure due to inappropriate implantation position and/or valve function.	VARC-2
Ventricular septal perforation	New ventricular septal perforation newly found during or after the study procedure by angiogram or echocardiography findings.	VARC-2

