7.2 Study Procedure

In this clinical trial, the investigational valve may be implanted by either TF, TA, or TAO approach. However, TF approach should be the first line of treatment, and when TF approach is difficult to perform, carefully examine the subject's clinical and anatomical characteristics, and then select appropriate access site (TA or TAO approach).

For deployment of the THV, the balloon should be inflated at a nominal volume (see Section 3.2 Table 3-2), and if dilatation at a nominal volume is impossible for medical reasons, the subject should be included in the bailout treatment registry (see Section 7.4 "Bailout Treatment Registry"). In the continued access registry, irrespective of whether the THV was implanted at a nominal volume or not, subjects who received the study procedure will be included in this registry. For preparation of study device, THV rinsing, and detailed implantation procedure, see Attachment 2 "Instructions for Use." In order to ensure and protect the

- 64 -

safety of the subjects, the sponsor should witness all procedures as much as possible and consider to be able to respond to questions about the study device and study procedure.

If severe aortic valve regurgitation is observed after implantation of the THV, a valve-in-valve procedure may be performed. When a valve-in-valve procedure is required, as a general rule, the study device should be used. Since sufficient evidence has not been obtained for the safety and efficacy of the valve-in-valve procedures, a physician who performs implantation should carefully select the size and perform the implantation procedure.

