9.2.2 Secondary efficacy endpoints

- Device success: 30 days after procedure
- Length of post-procedural hospitalization/ICU stay: At discharge
- NYHA classification: Post-procedure 30 days, 6 months, 1 year, and 2 to 5 years annually
- Six-minute walk test: Post-procedure 30 days and 1 year
- Quality of life (QOL) (EuroQOL, short form 12-item health survey [SF-12]): Post-procedure 30 days, 6 months, 1 year, and 2 to 5 years annually

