15.1.1.2 As-treated analysis set

A subject population consisting of subjects who were enrolled in this clinical trial and implantation of the study device was initiated is defined as as-treated (AT) analysis set. The time when invasion such as incision was made on the access site is regarded as the start of the study procedure. The primary endpoint and secondary safety and efficacy endpoints will be analyzed in the AT analysis set.

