15.1.1.3 Valve implant analysis set

The subject population consisting for all subjects in whom the THV was implanted, and when the subject exited the operation room the implanted THV was maintained is defined as valve implant (VI) analysis set. Subjects for whom the investigational valve was not implanted, including subjects switching to surgery, and TAVI bioprosthetic valve other than the investigational valve was implanted, will not be included in the VI analysis set. As for subjects who received a valve-in-valve procedure, cases with additional investigational valve implantation will be included in the VI analysis set, while cases with additional TAVI bioprosthetic valve other than the investigational valve will be excluded from the VI analysis set. The secondary valve performance endpoints based on the echocardiographic evaluation will be analyzed in the VI analysis set.

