Device deficiency	A device deficiency is defined as the failure of a device to meet its quality, safety, and performance specifications, such as damage and/or malfunctioning, regardless of being associated with the design, supply, storage, or used.	J-GCP
Valve malposition	Valve malposition includes moved valve, valve embolism, and implantation at an unintended site. For definition of events, see respective section.	VARC-2

Term	Definition	Reference/rationale
Moved valve	After a prosthetic valve was placed in an appropriate position, the valve moved upward or downward in the aortic annulus from the implanted site, with or without a causal relationship to the study procedure.	VARC-2
Valve embolism	The prosthetic valve moved during or after implantation, and no longer stay in the annulus.	VARC-2
Implantation at an unintended site	A prosthetic valve being persistently implanted at the site other than the aortic root.	VARC-2
Device success	
No operative death (death within 30 days post-procedure or death during hospital stay), the investigational valve was implanted at an appropriate anatomical position, and all intended performance of the investigational valve as shown in the followings were achieved.
 
 No prosthetic valve - patient mismatch Mean pressure gradient < 20 mmHg or maximum aortic flow velocity < 3 m/s No ≥ moderate aortic valve regurgitation 	VARC-2
Dry weight	The body fluid volume is proper, without excessive decrease in blood pressure during dialysis, and body weight with less burden on the cardiovascular system in a long-term basis.	Guidelines for evaluation and treatment of cardiovascular complication in hemodialysis patients
Dialysis conditions	
The dialysis conditions are as shown below:
 
 Number of dialysis per week (times/week) Duration of dialysis (hours) Blood flow (mL) Quantity of dialysate flow (mL) Removal method (filtration or diffusion) Dialyzer membrane type and membrane area With or without High Performance Membrane (HPM) dialyzer 	Guidelines for maintenance hemodialysis: Blood prescription

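### Device success has no single-valve or no-re-intervention condition, so a well-placed but severely leaking first study valve rescued with a second study valve scores as a success

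*Combined protocol and SAP*

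**What the plan says.** Section 30 (Glossary, Device success) lists three requirements.

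- Survival: "No operative death (death within 30 days post-procedure or death during hospital stay").
- Position: "the investigational valve was implanted at an appropriate anatomical position".
- Performance: "all intended performance of the investigational valve as shown in the followings were achieved". The items are no mismatch, mean gradient below 20 mmHg or peak velocity below 3 m/s, and no moderate or worse aortic regurgitation.

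Section 9.2.2 fixes the time point: "Device success: 30 days after procedure". Section 15.1.1.2 fixes the population: "The primary endpoint and secondary safety and efficacy endpoints will be analyzed in the AT analysis set".

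Section 7.2 foresees rescue: "If severe aortic valve regurgitation is observed after implantation of the THV, a valve-in-valve procedure may be performed". It adds that the study device should normally be used for this. The glossary describes a valve-in-valve procedure as one done "during or after the study procedure due to inappropriate implantation position and/or valve function".

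Section 15.1.1.3 does set a rule for such subjects, but only for the valve implant (VI) set. Subjects given an additional study valve stay in, while "cases with additional TAVI bioprosthetic valve other than the investigational valve will be excluded from the VI analysis set".

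**The concern.** A second valve placed because the first leaked severely means that the first device did not do its job. A measure called device success would be expected to record that. Here the assessment comes at 30 days, after any rescue done during the procedure, and none of the items asks how many valves were needed to reach the result. The authors considered valve-in-valve cases when they defined the VI set, but gave no matching rule for device success.

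At stake is the meaning of one reported percentage in a trial of 30 subjects. As written, it describes the result after any rescue, while a reader is likely to take it as the performance of one implanted device. The same subject could also be listed as a device success and as an aortic valve re-intervention, with nothing in the plan to explain the overlap.

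**Working it through.** **Step 1. Apply the written items to the possible cases.** In each rescue case, assume that the subject survives and that the 30-day echocardiogram is satisfactory.

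| Case | Survival | Position | 30-day performance | Result as written |
|---|---|---|---|---|
| First study valve well placed, severe leak, second study valve during the procedure | met | met | met | success |
| Same, but second study valve placed after the procedure and before the 30-day echo | met | met | met | success |
| First study valve malpositioned or embolised, second study valve placed | met | unclear: which valve is meant? | met | ambiguous |
| Rescue with a non-study valve | met | met if the first valve was well placed | unclear: the items refer to the study valve | not stated |
| Converted to surgery, no study valve implanted | met | not met | – | failure |

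The first two rows are the gap. No item in the definition can fail because of the rescue itself.

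**Step 2. Size per subject.** The plan states no figure for device success, so there is none to reproduce. Moving one subject from success to failure changes the rate by 1/n:

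- n = 30 (target, Section 4.3): 1/30 = 3.3 points
- n = 24 (evaluable number in the sample size calculation): 1/24 = 4.2 points

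As an illustration with an assumed starting count and exact (Clopper-Pearson) 95% intervals, 27/30 = 90.0% (73.5 to 97.9) becomes 26/30 = 86.7% (69.3 to 96.2) when one rescued subject is reclassified.

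**Step 3. How many subjects.** No second-valve rate is given. The nearest figures are the rates of implantation at the intended position in the US trial of the same device (Section 1.2.2.1): 99.4% transfemoral and 96.5% transapical. Their complements, 0.6% and 3.5%, serve only as a rough proxy for the rescue rate r.

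- Expected number, 30 × r: 30 × 0.006 = 0.18 and 30 × 0.035 = 1.05
- Chance of at least one, 1 − (1 − r)^30: 1 − 0.994^30 = 0.165 and 1 − 0.965^30 = 0.657

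This gives about 0 to 1 subject, with a 17% to 66% chance of at least one. The expected shift in the rate is 30 × r × (1/30) = r, or 0.6 to 3.5 points, if every such subject otherwise passes. The EU trial's transfemoral rate of 98.2% lies inside this range (30 × 0.018 = 0.54 expected, 42% chance of at least one). The transaortic group in the US trial and the combined transapical/transaortic group in the EU trial had 100%.

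**Step 4. Primary endpoint.** The stated power reproduces. With 24 subjects, an exact one-sided test of 45% rejects at 6 or fewer deaths; its actual level is 0.0364 and its power at 20% mortality is 0.8111, against the stated 81.1%. No input to this calculation involves device success.

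**The case against.** The strongest reply is that the definition is not blind to failure and that the event is visible elsewhere. Operative death and valve position count as well as the final haemodynamic result. A malpositioned first valve can be read as failing the position item. Conversion to surgery without a study valve already fails. Aortic valve re-intervention and nonstructural valve dysfunction are secondary safety endpoints (Section 9.2.1), and their glossary definitions are broad enough to cover a rescue. Both are analysed in the as-treated set. All of this stands, but none of it changes the classification of a well-placed, severely leaking first valve. Nor does the plan say whether a second valve during the index procedure is a re-intervention.

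A reader might go further and infer three things that the documents do not support.

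- *That the failed implant is hidden from every valve-performance result, or that the rules always favour the device.* The VI exclusion removes nobody from device success, which uses the as-treated set. A rescue after the procedure may be preceded by a scheduled echocardiogram that shows the first valve. Leaving another manufacturer's or model's valve out of study-valve haemodynamics is defensible.
- *That the rate is overstated by as much as 10 points.* That needs three rescued subjects in 30, for which the documents give no basis.
- *That the 30-day regurgitation table could be rebuilt with the grade that triggered rescue.* Section 10.2.2 schedules readings just before and just after the procedure, and Section 10.1 ends the procedure at access-site closure. The reading after an intraprocedural rescue is therefore taken with both valves in place. The core laboratory's listed time points (Section 13.2) do not include procedural images.

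It is also fair to say that Section 15.1.2 leaves detailed methods to a Statistical Analysis Plan. The combined document supplied for review contains no rule there on this point, but one may exist in text not supplied.

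**Conclusion.** The gap is real and narrow. Under the written definition, a subject whose well-placed first study valve leaked severely and who was rescued with a second study valve before the 30-day assessment is a device success, provided the subject survives and the post-rescue echocardiogram is satisfactory. Each such subject adds 3.3 points to the rate with 30 subjects.

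The total effect is an assumption. The proxy of about 0 to 1 subject comes from non-dialysis patients and measures position, whereas the clear gap concerns leakage in a well-placed valve. It indicates the order of magnitude and is not an estimate. One subject's shift is small beside an exact interval about 24 points wide (97.9 − 73.5), but it is a known direction of misclassification and can be removed by wording. Device success is descriptive and untested, and the conclusion on 1-year mortality does not depend on it.

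**What to change.** Make three wording changes.

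1. In the glossary definition, add that a subject who receives a second valve (study or other), or who has an aortic valve re-intervention before the 30-day assessment, is not a device success.
2. State whether a second valve placed during the index procedure counts as an aortic valve re-intervention.
3. Report the number of valve-in-valve cases in the as-treated set.

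No clause on surgical conversion is needed, because that already fails when no study valve is implanted. The valve implantation and device information collected under Section 10.2.2 should supply the count. Section 15.4 already provides for recording the change and its reason. Because enrolment in the main set is closed in this version, the rate should be given on both definitions if outcomes have already been seen. The only real cost is a device success rate that may be slightly less favourable.

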9.2 Secondary Endpoints

9.2.1 Secondary safety endpoints

- Composite endpoint: Post-procedure 30 days, 6 months, 1 year, and 2 to 5 years annually
 - Death and stroke
- Single endpoints: Post-procedure 30 days, 6 months, 1 year, and 2 to 5 years annually
 - Death (cardiovascular, non-cardiovascular)
 - MI (periprocedural, spontaneous)
 - Stroke (disabling, non-disabling)
 - Bleeding (life-threatening or disabling, severe, mild)
 - Vascular access site/access-related complications
 - Severe vascular complications
 - Conduction disorder/arrhythmia
 - Conduction disorder requiring new pacemaker implantation
 - Aortic valve re-intervention
 - Coronary obstruction
 - Endocarditis
 - Valve explants
 - Structural valve deterioration
 - Nonstructural valve dysfunction

Table 10-1: Permissible time windows for the tests/observations

Test/observation timing	Baseline ^{a)}	Procedure ^{b)}	Immediately after procedure	Post-procedural follow-up observation		
				Hospital discharge	30 days post-procedure	6 months post-procedure
Reference date (time)	-	Day 0	Up to 72 hours after exiting the operation room	7 days post-procedure or hospital discharge, whichever comes earlier	30 days post-procedure	182 days post-procedure
Permissible time window	Within 60 days pre-procedure	-	-	± 2 days	-7 days/+14 days	± 30 days

^{a)} The 12-lead ECG should be performed within 48 hours prior to entering the operation room, clinical laboratory tests within 14 days prior to the procedure, and coronary angiography and aortofemoral blood vessel evaluation (CT, MRI, or X-ray) within 90 days pre-procedure (see Section 10.2.1 "Baseline"). For the continued access registry, except cases that may be clinically valid, coronary angiography should be performed within 1 year prior to the study procedure.

^{b)} Cardiac catheter test at procedure should be performed immediately before and after the procedure.

Table 10-2: Permissible time windows for the tests/observations

Test/observation timing	Post-procedural follow-up observation				
	1 year post-procedure	2 years post-procedure	3 years post-procedure	4 years post-procedure	5 years post-procedure
Reference date	365 days post-procedure	730 days post-procedure	1095 days post-procedure	1460 days post-procedure	1825 days post-procedure
Permissible time window	± 30 days	± 45 days	± 45 days	± 45 days	± 45 days

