- Laboratory tests (to be performed within 14 days pre-procedure)
 - Hematology
 - Red blood cell count, hemoglobin, hematocrit, platelet count, white blood cell count, differential white blood cell count (neutrophil, lymphocyte, monocyte, eosinophil, basophil)
 - Biochemistry
 - Sodium, potassium, creatinine, urea nitrogen, albumin, total bilirubin, CRP, GOT(AST), GPT(ALT), LDH, hemoglobin A1c, glycated albumin, phosphate, calcium
 - Coagulation
 - Prothrombin time, activated partial thromboplastin time
 - Cardiac enzyme
 - CK and troponin, or CK-MB and troponin
- Echocardiography

Perform echocardiography in reference to the Echo Core Laboratory Procedure to measure/evaluate the following items. The resulted echocardiographic images should be submitted to the Echo Core Laboratory.

[Measurements/endpoints]

Cardiac output, aortic valve pressure gradient (mean/maximum), AVA, AVA index, aortic valve regurgitation (severity/regurgitation site), aortic annulus diameter*, maximum aortic flow velocity, LVEF, left ventricular mass, LVMI, valvular and paravalvular conditions

* The aortic annulus diameter should be estimated from the left ventricular outflow tract (LVOT) dimension.
- Cardiac CT

[Measurements/endpoints]

Aortic annulus diameter, aortic annulus area, distance from aortic annulus to coronary ostium
- Coronary angiography (to be performed within 90 days pre-procedure)
 - If a subject has no hypersensitivity to contrast media, but contrast media cannot be used due to other disease, MRI may be used.
- Aortofemoral vascular evaluation (to be performed within 90 days pre-procedure)

Perform CT, MRI, or X-ray to evaluate from the aorta through to the femoral artery.
- QOL questionnaire
 - EuroQOL (see Appendix 4)

- SF-12 (Appendix 5)
- Anticoagulant/antiplatelet drugs (to be investigated from 7 days prior to the procedure)
- Antibiotics (to be investigated from 7 days prior to the procedure)
- Blood purification

Investigate the latest dialysis prior to the procedure.

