10.2.3 Immediately after procedure

The test/observation immediately after the procedure will collect the data on the following items until 72 hours after exiting the operation room.

- 12-lead ECG
- Chest X-ray

- Cardiac enzyme test (CK and troponin, or CK-MB and troponin)
 - Anticoagulant/antiplatelet drugs
 - Antibiotic
 - Blood purification
 - Other concomitant medication/therapy
 - AE/device deficiency
- For a patient who has suffered a stroke, mRS must be evaluated within 30 to 90 days and beyond 90 days as earlier as from the onset of stroke.

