Myocardial Infarction	
When meeting any one of the followings, it is defined as myocardial infarction.
 
 Periprocedural myocardial infarction (within 72 hours post-procedure) 
 When meeting both of the following criteria, it is regarded as periprocedural myocardial infarction. 
 Newly developed ischemic symptoms (chest pain, shortness of breath, etc.) or signs (ventricular arrhythmia, newly developed or worsened heart failure, new ST change, unstable hemodynamics, newly developed abnormal Q-wave ≥ 2 leads, new imaging information of normal myocardial loss, or regional wall abnormal motion) CK-MB within 72 hours post-procedure > 5 times the upper range limit (URL), or troponin > 15 times. Idiopathic myocardial infarction (72 hours post-procedure) 
 When meeting any one of the following criteria, it is regarded as idiopathic myocardial infarction. 
 Elevation of CK-MB or troponin over the reference standard, together with at least one of the following findings: 
 Symptoms of ischemia ECG changes indicative of new ischemia (ST-T changes, LBBB) Newly developed abnormal Q-wave at \geq sequential 2 leads Imaging evidence of a new loss of viable myocardium or new wall motion abnormality. Unexpected sudden death including cardiac arrest (developing symptoms primarily suggestive of myocardial ischemia, with new ST elevation or new LBBB, and/or death before blood sampling or development of myocardial biomarker in blood, with a newly developed clot by angiogram and autopsy. Pathological findings of acute myocardial infarction 	VARC-2														
NIHSS	Neurological severity scale for stroke developed by National Institutes of Health (NIH). (see Appendix 1 "NIHSS")	NIH														

Term	Definition	Reference/rationale								
Non-structural dysfunction	Although abnormality is not of the prosthetic valve itself (namely the valve structure is normal), abnormality leading to stenosis regurgitation. Non-structural dysfunction includes pannus formation, proliferation of own tissues, engulfed suture, paravalvular regurgitation, inappropriate sizing or implantation position, residual leakage or obstruction after implantation of the valve, and clinically significant hemolytic anemia. (see "Paravalvular regurgitation")	STS/AATS								

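### The late (spontaneous) MI definition asks for no change from the subject's own earlier marker value and no new symptoms, so stable angina with an unchanged raised troponin meets it

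*Combined protocol and SAP*

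**What the plan says.** Section 9.2.1 lists "MI (periprocedural, spontaneous") among the secondary safety endpoints at 30 days, 6 months, 1 year and annually from year 2 to year 5. The Section 30 glossary entry for myocardial infarction calls the late category idiopathic, not spontaneous, and makes its criteria alternatives: "When meeting any one of the following criteria, it is regarded as idiopathic myocardial infarction". The first alternative is "Elevation of CK-MB or troponin over the reference standard, together with at least one of the following findings". The item at the head of that list is simply "Symptoms of ischemia".

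The periprocedural category needs both a clinical and a biomarker condition. The biomarker condition is "CK-MB within 72 hours post-procedure > 5 times the upper range limit (URL), or troponin > 15 times".

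Section 10.2.1 collects "CK and troponin, or CK-MB and troponin" within 14 days before the procedure. The same enzymes are scheduled at discharge, 30 days, 6 months and 1 year (Sections 10.2.4 to 10.2.7). Neither MI definition refers to these earlier values. Section 13.1 limits committee adjudication to deaths and strokes up to 1 year. Section 15.1.2 makes all secondary endpoints descriptive.

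**The concern.** A definition that compares a marker with a population limit works when subjects normally sit below that limit. For a subject who sits above it without infarction, the biomarker half carries no information because it is met at every draw. Classification then depends entirely on the accompanying finding, and the weakest one allowed is ischemic symptoms with no requirement that they be new.

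The visit schedule makes this a practical matter. CCS angina class and cardiac enzymes are collected together at discharge, 30 days, 6 months and 1 year, so a subject with long-standing angina and a stable raised troponin can satisfy the wording at a routine visit, without any acute episode. Section 1.1.2 notes that coronary artery disease is frequent in dialysis patients. If sites differ in how literally they apply the wording, the same patient could be an MI at one site and not at another, with no central review to align them. In a cohort of 30, whose 1-year report supports the approval application (Section 18.3), a few such cases would dominate the MI line.

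**Working it through.** The plan states no MI rate and no MI-based calculation, so there is no plan figure to reproduce. The check is a reading of the definition, followed by simple arithmetic on its consequence.

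1. **Is a change required for the late biomarker?** No. The threshold is the reference standard itself. There is no multiple of the limit, no rise or fall between samples, and no rule for a subject already above it.

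2. **Must the accompanying finding be new?** Set side by side, the glossary items are:
   - late ECG change: must indicate new ischemia;
   - late Q-wave: must be newly developed;
   - late imaging finding: new loss of myocardium or new wall motion abnormality;
   - periprocedural symptoms: must be newly developed;
   - late symptoms: no such condition.

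   The late symptom item is the only one without it.

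3. **Does another section supply the missing rule?** Section 11.3 speaks of abnormal variations from baseline, but only to decide when a laboratory result is an adverse event. Section 11.6 asks sites to enter a diagnosis where possible. Neither amends the MI definition, and Section 13.1 does not bring MI before the committee. Other endpoints do refer to the prior state: disabling stroke needs a worsening of at least 1 on the mRS from before onset, and structural valve deterioration refers to a worsening of at least 1 NYHA class.

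4. **Worked case.** Suppose troponin is 3 times the limit at baseline and again at 6 months, with unchanged angina throughout. The marker is over the limit and ischemic symptoms are present. The written definition is met although nothing has changed.

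5. **Effect per subject**, taking the target of 30 (Section 4.3) as denominator: 1/30 = 3.3%, exact 95% CI 0.1% to 17.2%. Three such subjects give 3/30 = 10.0%, exact 95% CI 2.1% to 26.5%.

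6. **How many subjects?** The documents give neither input. As an assumption only, let q be the share with a stable marker above the limit and s the share with ischemic symptoms but no infarction after 72 hours. If the two are independent, the expected number of false late MIs is 30 × q × s:
   - q = 0.1, s = 0.05: 30 × 0.1 × 0.05 = 0.15;
   - q = 0.5, s = 0.10: 30 × 0.5 × 0.10 = 1.5;
   - q = 1.0, s = 0.30: 30 × 1.0 × 0.30 = 9.0.

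   The result spans a factor of 60 (9.0/0.15), so it is not an estimate. The baseline troponin values already collected would replace the assumption about q with a count.

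**The case against.** The strongest reply is that symptoms of ischemia are a clinical judgment, that sites record diagnoses, and that an investigator would not call an unchanged value with unchanged angina an infarction. That may well happen, but no written rule directs it, so it does not remove the gap. It does mean the point concerns what meets the definition, not what sites have reported.

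A second reply is that MI is descriptive, lies outside the primary endpoint and the death-and-stroke composite, and that over-counting works against the device. This is correct and limits the importance of the point. A safety rate should still describe what it names.

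A third reply is that narrowing a safety endpoint after main-cohort enrollment has closed, in an open single-arm trial, carries its own risk of bias. This also stands, and it rules out replacing the definition.

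A reader might infer more than the documents support:
- **That dialysis subjects in general will be labelled MI, by a known amount.** The background sections say nothing about troponin levels in dialysis or aortic stenosis, so the point is conditional on the marker being above the limit.
- **That the MI rate cannot be compared with the cited non-dialysis trials.** The summaries in Section 1.2.2.1 report no MI rate, and no such comparison is planned.
- **That troponin will often be the only qualifying marker.** The protocol allows CK in place of CK-MB but gives no frequency.
- **That the periprocedural definition has the same problem.** It too ignores the baseline value, but it requires new symptoms or signs and a much higher threshold; nothing shows that the omission matters there.

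**Conclusion.** The point holds as a gap in the late-MI definition. For any subject whose CK-MB or troponin already exceeds the reference limit, unchanged ischemic symptoms are enough to count as MI, and no other section or committee corrects this. Each misclassified subject adds 3.3 percentage points at 30 subjects. The number of such subjects is unknown from the documents. The primary mortality comparison, the stated 81.1% power and the sample size do not depend on the MI definition and are unaffected. The point is a worthwhile and fairly cheap improvement to one descriptive safety endpoint.

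**What to change.** Keep MI as currently defined and report it. Add to the SAP, through the revision procedure in Section 15.4, a supplementary baseline-referenced late-MI count:

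- The reference value is the baseline value or the latest scheduled value at 30 days, 6 months or 1 year. Do not use the discharge value, taken within about a week of the procedure, when procedural marker release may not have settled.
- If the reference value already exceeds the limit, the biomarker arm counts only with both (a) new or worsened ischemic symptoms or another listed new finding, and (b) an increase over the reference value by a threshold fixed before the events are reviewed. The documents supply no threshold, so the sponsor must choose and justify one.
- Report both counts, and flag events without a usable pair of values as not evaluable.
- Report how many subjects had a baseline marker above the limit.
- Reconcile the terms spontaneous (Section 9.2.1) and idiopathic (Section 30).

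The cost is a short SAP addition and some data retrieval; no new scheduled tests are needed. Cardiac enzymes are not listed for unscheduled visits (Section 10.2.10) or for years 2 to 5 (Section 10.2.8), so event values there may have to come from source records. In the later years the reference value would be the 1-year value at best, and therefore up to 4 years old. Because the addition comes after main-cohort enrollment closed (Section 27), it must remain supplementary.
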